657 that receive the peer PrEP referral + HIVST intervention delivered by the peer providers. For reporting
658 purposes, we will also refer to peer providers as “index peers” and peer clients as “referred peers.”

659 We will recruit 80 young female peer providers from public healthcare clinics delivering PrEP in Kiambu
660 County and neighboring Counties using established PHRD site techniques. These participants will further
661 refer 4 peer clients each to PrEP for a maximum 320 potential peer clients.

662 Eligibility criteria.

663

664 **Peer providers.** Eligible peer providers will be: i) female, ii) ≥ 16 to 24 years old (including emancipated
665 minors ≥ 16 to 17 years³⁶), iii) must have refilled or initiated PrEP (i.e., been dispensed PrEP), iv) are able
666 to identify 4 peers at risk of HIV infection who may be interested in PrEP, v) not currently enrolled in
667 another HIV study, and vi) are able and willing to be randomized to the intervention, complete research
668 activities, and provide written consent (**Table 6**). Due to the nature of the training intervention which
669 includes slides, quizzes, and other activities that involve reading and writing, peer providers will be
670 considered ineligible if they do not have basic literacy skills. Due to some challenges recruiting young
671 female peer providers in the Aim 1 pilot, we made some modifications to the inclusion criteria in this
672 section, including reducing the duration of PrEP use and dropping the requirement for PrEP disclosure.

673

674 **Peer clients.** Eligible peer clients will be: i) female, ii) ≥ 16 to 24 years old (including emancipated minors
675 ≥ 16 to 17 years³⁶), iii) referred by a peer provider to initiate PrEP, and iv) are able and willing to provide
676 informed consent.

677

678 **Recruitment strategies.** **Peer providers.** Peer providers will be recruited through a multipronged approach
679 that will include recruitment through other ongoing PrEP research projects, and from nearby public health
680 facilities implementing PrEP programs, such as, workshops for healthcare workers, use of IEC materials,
681 and working with community health workers to identify potential participants. Peer providers will be

682 compensated 300 KES (~\$2.70 USD) and be reimbursed for travel at their baseline appointment and
683 again at their 3-month follow-up appointment. No travel reimbursement at follow-up will be provided if

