684 follow-up questionnaires are conducted via phone. All peer providers will be encouraged to disclose PrEP
685 use to peers, although this is not required. Study counselors will conduct follow-up calls with peer
686 providers to check in and see how the referral process is going and answer any questions or concerns
687 regarding the intervention. Recruitment of peer providers will be on a rolling basis, so it is possible that
688 peer providers and peer clients may not be mutually exclusive (as future peer providers could be previous
689 peer clients).

690 *Peer clients.* Peer providers will recruit peer clients. Peer clients will contact study counselors (via phone),
691 to provide RAs with contact information to schedule a follow-up visit (Month 3) at the PHRD study site
692 (transport refunded) or via phone interview. Clients won't be engaged in study activities at Month 3 until
693 they have provided informed consent. To help prompt peer providers to remind peer clients to call
694 research staff at the point of recruitment (a challenge during the pilot study), we will compensate peer
695 providers and their peer clients a small amount (150 KES each, ~\$1.40 USD each) each time a peer
696 client pings the study phone line to enroll in the study. For any peer clients who do not ping the study
697 phone, study staff will attempt to collect contact information for the peer clients from the peer providers
698 during a follow-up visit/call. The peer client can still decline enrollment when contacted by study staff.
699 Peer clients will be compensated 300 KES (~\$2.70 USD) and reimbursed for travel for attending the 3-
700 month follow-up appointment. No travel reimbursement will be provided if the questionnaires are
701 conducted over the phone. To facilitate the delivery of this compensation, we will use a secure mobile
702 money platform (M-Pesa) that we have used successfully for other research projects. Research staff will
703 call these individuals twice (one week apart) and stop trying to contact these potential participants if these
704 phone calls do not go through. Additionally, they will do their best to confirm the identity of the potential
705 peer client before describing any details of the research study (and their potential participation in this
706 study).

707

708 Consenting procedures. *Peer providers.* All peer providers that meet eligibility requirements will provide

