709 written informed consent at the point of recruitment and prior to randomization with a trained research
710 assistant. This signed consent form will be stored as confirmation of informed consent and a copy will be
711 made available to the participant.

712 *Peer clients.* All peer clients that have contacted the study team directly, expressed interest in the study,
713 and have met eligibility requirements will complete informed consent at the Month 3 follow-up visit, before
714 completing any questionnaires assessing their experience with the peer PrEP referral + HIVST
715 intervention or informal peer PrEP referral process. Those unable or unwilling to come to the PHRD site
716 to sign a consent form will have the option to provide verbal consent over the phone. If verbal consent
717 was provided, the trained research assistant will note the date that verbal consent was obtained on a
718 copy of the consent script. The signed consent form and scripts will be stored as confirmation of informed
719 consent. A subset of peer clients who sign the written consent form will also be asked to provide a DBS
720 sample collected from a finger prick or venous blood. No peer client providing verbal consent will be
721 asked to provide a DBS sample.

722

723

Table 6. Eligibility and recruitment strategies- randomized trial

	Eligibility	Ineligibility	Recruitment Strategies
Peer providers (formerly “PrEP users”) (n=80)	
 • ≥ 16- 24 years old³⁶ • Female • Must have refilled or initiated PrEP (i.e., been dispensed PrEP) • Not currently enrolled in an HIV study • Can identify 4 peers at HIV risk who could benefit from PrEP • Able & willing to be randomized to the intervention, participate in research activities, and/or provide written informed consent 	
 • Not between 16-24 years old • Male • Have not used PrEP • Cannot identify 4 peers who would benefit from PrEP • Is not able or willing to be randomized to the intervention, participate in research activities, and/or provide written informed consent • Currently enrolled in an HIV study • Illiterate 	
 • Recruit participants from HIV clinics where PrEP is available using PHRD recruitment strategies (e.g., workshops for healthcare workers) • Strategies developed and refined during the pilot study

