 820 contact information directly to the study team and request to be enrolled in the study will be contacted to
 821 schedule an interview at Month 3. The peer client will be screened for eligibility and consented prior to
 822 completing a follow-up survey at Month 3. This timeline will provide recruited peer clients with the
 823 opportunity to enroll in PrEP (approx. 1 month following the baseline survey) and return to healthcare
 824 facilities for one PrEP refill (approx. 3 months following the baseline survey). Sociodemographic
 825 information will be collected at baseline among peer providers and follow-up among peer clients (i.e.,
 826 their first research visit). At all follow-up visits, we will measure both self-reported outcomes related to
 827 adoption of PrEP services, as well as process-level outcomes (e.g., number of HIVST kits received in the
 828 intervention arm, PrEP referral cards received in both arms), and implementation outcomes (e.g.,
 829 intervention acceptability, appropriateness, fidelity, satisfaction).

Fig. 8. Timeline for the Aim 3 randomized trial.

831 **Setting.** Experienced quantitative researchers will collect electronic data using CommCare (Dimagi,
 832 Cambridge, USA), an electronic data collection tool, in questionnaires at baseline (Month 0) and follow-
 833 up (Month 3). While we will encourage all enrolled peer clients to come to the PHRD research site to
 834 complete the questionnaires in person, we will additionally allow for the option of questionnaire
 835 participation/completion over the phone to allow for easier engagement in follow-up activities (in
 836 particular, peer clients that might have been recruited outside of Kiambu County). Peer providers will
 837 need to come in-person to the clinic during baseline to receive the intervention they are randomized to.
 838 All participants will receive 300 KES (~\$2.70 USD) for their time and effort completing each study
 839 visit/questionnaire. For participants completing questionnaires remotely via the phone, we will send this
 840 reimbursement via a secured mobile money platform (i.e., M-Pesa), as we have done routinely for other
 841 projects. For participants that come to the PHRD research site to complete these visits/questionnaires in
 842 person, we will additionally provide reimbursement for transportation.

843 **DBS samples.** At follow-up (Month 3) DBS samples will be collected from peer clients to validate PrEP

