## 3. Study overview and objectives

### 3.1. Study overview

**Table 1. Overview of the Peer PrEP cRCT components**

[figure not shown]
Protocol title:	Peer PrEP referral + HIV self-test delivery for PrEP initiation among young Kenyan women: randomized implementation trial
Short title:	Peer PrEP Study
Design:	This study is a hybrid effectiveness-implementation randomized trial
Population:	We will enroll two different population types in this study: 1. Index peers : (Also called PrEP users or peer providers in our formative research and pilot study). Adolescent girls and young women ≥16-24 years  old using PrEP for at least one month in the past 12 months.

	
2. Referred peers: (Also called peers or PrEP clients in our formative research and pilot study). Female peers <math>\geq 16</math>-24 years old of the index peer whom the index peer thinks has behaviors associated with HIV risk and may be interested in and benefit from daily oral PrEP.
 
16- and 17-year-olds must be emancipated minors; all participants must be able and willing to provide informed consent.

Randomization:	1:1 enhanced group: standard group

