**Table 4. Detailed description of Peer PrEP cRCT process outcomes**

Process outcomes	Definition	Reported by	Timing
Peers referred	Number clients referred to PrEP services by index peers	Index peers	Month 3
HIVST use	% of referred peers in the enhanced group that used an HIVST (once; twice; or for partner testing)	Referred peers	Month 3
Client linkage to care	% of referred peers that went to a clinic to access HIV prevention/treatment services, among those referred	Referred peers	Month 3

Note: All outcomes binary.

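### A woman referred in the enhanced arm can later be randomised to lead a control cluster, and no stated variable, ID link or analysis identifies her

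*Protocol*

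**What the plan says.** The Protocol's Aim 2 text on recruitment states the premise itself: "Recruitment of peer providers will be on a rolling basis, so it is possible that" the two roles overlap, and "peer providers and peer clients may not be mutually exclusive (as future peer providers could be previous" clients.

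Three eligibility statements bear on whether a referred peer can become an index peer:

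- The PrEP criterion in Protocol Table 6, repeated in SAP Table 2, is "Must have refilled or initiated PrEP (i.e., been dispensed PrEP"). A referred peer who starts PrEP meets it. SAP Table 1 describes index peers differently, as "using PrEP for at least one month in the past 12 months".
- Protocol Table 6 requires "Not currently enrolled in an HIV study", and SAP Table 2 has the same rule. The Protocol's running text limits the bar to "another HIV study, and vi) are able and willing to be randomized to the intervention".
- Referred peers give consent only at Month 3 (Protocol, Consenting procedures).

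Protocol Table 7 gives enhanced-arm clients the formalised conversation, the brochure and HIVST kits. Control index peers are meant to receive none of these. The one-day training and the WhatsApp group go to enhanced index peers only.

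SAP Table 7 numbers index peers (03) and referred peers (04) in separate sequences. The Protocol's Implementation outcomes paragraph and the Fidelity row of SAP Table 5 plan a checklist, completed by referred peers in both arms, of the materials they received. HIVST use, by contrast, is the percentage "of referred peers in the enhanced group that used an HIVST" (SAP Table 4).

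**The concern.** The trial compares formal with informal referral, so the contrast depends on control index peers referring in their usual way. Index peers are recruited from public clinics that deliver PrEP in Kiambu and neighbouring counties, and the referral card sends clients in both arms to clinics of that kind. The SAP's note to Table 2 places one change six months into implementation, against a follow-up of three months. There was therefore time for a referred peer to start PrEP and be recruited as an index peer.

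Allocation is 1:1 in blocks of 4, with no stratification by earlier referral stated. A former enhanced-arm client thus has about an even chance of being assigned to control. If her earlier exposure makes her a more effective referrer, control initiation rises and the primary difference shrinks. She also contributes an outcome to the cluster in which she was referred and leads a second cluster, while the model in SAP section 10.2 has only an index-peer random effect and treats the two as independent.

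The Limitations, the sample-size sections, SAP section 10.2 and the sensitivity analyses in SAP section 10.4 do not mention dual roles. If the trial finds a small effect, the reader could not tell how many control clusters were led by such women.

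**Working it through.** **Inputs from SAP section 5.1:** 40 clusters per arm, 3 referred peers per cluster, ICC 0.05, initiation 63% (standard) v 80% (enhanced), stated power 80%. **From the Protocol's Statistical analysis section:** two-sided 0.05.

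**The plan's own figure.** Design effect = 1 + (3 − 1) × 0.05 = 1.10. Effective n per arm = 40 × 3 / 1.10 = 109.1. For a two-proportion z test with pooled variance under the null:

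power = Φ{ [ (p2 − p1) − 1.96 √(2 p̄(1 − p̄)/n) ] / √( [p1(1 − p1) + p2(1 − p2)]/n ) }

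With p1 = 0.63, p2 = 0.80, p̄ = 0.715 and n = 109.1, this is Φ[(0.170 − 0.120)/0.060] = 79.9%. The stated 80% is reproduced. It assumes no contamination.

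**Dilution.** Two quantities are assumptions, since neither document gives them:

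- f is the share of control clusters led by a former enhanced-arm referred peer.
- c is the share of the intervention effect that she carries over.

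Control initiation becomes 0.63 + f × c × 0.17. The enhanced rate stays at 0.80.

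| f | c | Control rate | Difference (points) | Power |
|---|---|---|---|---|
| 0 | – | 63.0% | 17.0 | 79.9% |
| 5% | 0.5 | 63.4% | 16.6 | 78.0% |
| 10% | 0.5 | 63.85% | 16.2 (16.15) | 76.0% |
| 10% | 1 | 64.7% | 15.3 | 71.7% |
| 20% | 1 | 66.4% | 13.6 | 62.2% |

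**What these values of f mean.** Under 1:1 randomisation, f is expected to equal the share of all 80 index peers who are former enhanced-arm clients: 5% is 4 women (2 in control) and 10% is 8 (4 in control). The 20% row is 16 women. If former control-arm clients entered as well, in proportion to the 63:80 initiation rates, former clients of either arm would be 20% × (1 + 63/80) = about 36% of all index peers. Nothing in the documents supports that, so the last row only marks an outer range.

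**What can carry over.** From Protocol Table 7, a former enhanced-arm client has had the conversation, the brochure and her own kits. She has not had the training or the WhatsApp group, and as a control index peer she receives no brochures or kits to hand out. Full carry-over (c = 1) is therefore an upper bound.

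**The reverse path.** A control-arm client could be recruited and randomised to the enhanced arm before her own Month 3 outcome is reported. To qualify she must already have been dispensed PrEP, and dispensing is the primary endpoint (SAP section 4.1). Her initiation therefore precedes her training, unless she had been dispensed PrEP before being referred. Continuation and adherence can be affected; initiation generally cannot.

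**The case against.** The strongest reply has four parts.

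**The trial may already exclude active clients.** The wording in Protocol Table 6 and SAP Table 2 lacks the word 'another', so it could be read to bar a woman currently in this trial. This stands only in part. Referred peers consent at Month 3, so it is unclear whether a woman counts as enrolled before then, and one who has finished is not currently enrolled. The Protocol's own statement that roles may overlap shows that the rule was not meant as a general bar.

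**The data can show contamination.** A reader might infer that the planned data could not reveal any carry-over, from the separate ID sequences and from the Protocol's example of kits counted in the "intervention arm, PrEP referral cards received in both arms". The documents do not support that. The both-arm checklist would show brochures or kits reaching control referred peers who are followed up. Contact details, locator forms and ID-linking lists are also kept, so manual matching may be possible. The contents of the Aim 2 baseline questionnaire are not listed, so an item on referral history cannot be ruled out. What remains is narrower: the checklist records what clients received, not the index peer's own earlier exposure. A former client in control has no brochures or kits to distribute, so a carried-over way of talking about PrEP would leave no trace there.

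**The overlap may be rare.** This stands. With f = 5% and half carry-over, the loss is about 2 points of power.

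**Randomisation is not broken.** This also stands. For the cluster she later leads, earlier referral is a characteristic fixed before allocation and balanced in expectation. It blurs the contrast; it does not bias the allocation.

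**Conclusion.** The point holds as a cheap improvement. The Protocol allows a woman referred in this trial to be randomised later as an index peer, and no criterion clearly prevents it. Neither document states a variable, an ID link or an analysis that would identify her. The expected bias is towards no difference, on the assumption that earlier enhanced exposure improves her referrals. The size is unknown because f and c are not given: over f = 5–10% with half carry-over, the 17-point difference becomes 16.6 to 16.2 points and power 78% to 76%. With full carry-over at f = 10%, it becomes 15.3 points and 72%. The effect of linked clusters on the standard error was not quantified.

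Two stronger readings should be avoided. The documents do not show that carry-over happened, only that it is possible. Nor does the reverse path, from control client to enhanced index peer, generally alter the primary outcome.

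**What to change.** 1. **At index-peer screening, before randomisation,** ask whether the woman has already been referred in this trial, and record the referrer's ID and arm. Exclude these women or, if recruitment does not allow that, flag them.
2. **In the data,** link 03 and 04 IDs. For women already enrolled, do this from retained contact and locator records where possible. Report the overlap by arm. If enrolment has closed, this and the next step are the parts still available.
3. **In SAP section 10.4,** add a sensitivity analysis of the primary outcome that drops clusters led by a former referred peer, in both arms. The status is fixed before that index peer's allocation, so the remaining comparison is still between randomised groups.
4. **Do not** drop referred peers who later became index peers. They must have been dispensed PrEP to qualify, so the exclusion would remove almost only successes and would depend on the outcome.
5. **Reconcile** the index-peer PrEP criterion in SAP Table 1 with SAP Table 2, and the two wordings of the HIV-study rule, since both affect whether and how soon a referred peer could qualify.

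The both-arm checklist needs no change for this purpose; the residual gap is HIVST use, which is defined for the enhanced group only and could be asked in both arms.

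Cost: one screening question, one linking variable and one sensitivity analysis. If women are excluded, a few potential index peers are lost, in a trial whose Protocol reports difficulty recruiting them in the pilot. Flagging avoids that loss.
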